8.3.3 Analysis of Tertiary Efficacy Variables

8.3.3.1 Definition of Variables

For the normalization of annual period the following formula will be used: Normalized Variable = Variable $\times 365.25 / (\text{date of last dose} - \text{date of first dose} + 1)$.

The time-to-first pulmonary exacerbation (in days) is calculated as: first pulmonary exacerbation date (postdose in the current study) – first dose date + 1.

The time-to-first CF-related hospitalization (in days) is calculated as: first CF-related hospitalization date (postdose in the current study) – first dose date + 1.

Weight-for-age z-scores, length-for-age z-scores, weight-for-length z-scores, and BMI-for-age z-scores will be derived from weight, length, and BMI values using the WHO Child Growth Standards for infants and children¹, for whom population norms are available from 0 to 60 months of age. The same growth standards will be used to calculate percentiles for each measure.

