### 8.1 Ivacaftor Arm: Subjects From Study 124 Part B

#### 8.1.1 Inclusion Criteria

1. Subjects transitioning from Study 124 Part B must have completed the last study visit of Study 124 Part B

Added guidance:

- Subjects who had a study drug interruption at the last scheduled visit of Study 124 Part B, subjects who required study drug interruption that was to be continued or initiated at Day 1 in Study 126, or subjects who resumed study drug in Study 124 Part B after a study drug interruption due to elevated transaminases but who did not complete at least 4 weeks of rechallenge with study drug (due to the timing of the rechallenge versus the time remaining in Study 124 Part B) must meet eligibility criteria and have received approval from the Vertex medical monitor.
2. For Gap Transition subjects: hematology and serum chemistry results at baseline with no clinically significant abnormalities that would confound the study assessments or pose an additional risk to administering ivacaftor to the study subject, as judged by the investigator.
  3. As judged by the investigator, parent or legal guardian must be able to understand protocol requirements, restrictions, and instructions; and must sign the informed consent form (ICF).

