#### 8.2.1 Inclusion Criteria

1. Age <24 months at the Day 1 Visit
2. Confirmed diagnosis of CF, defined as a sweat chloride value  $\geq 60$  mmol/L by quantitative pilocarpine iontophoresis or 2 CF-causing mutations
  - If the results of the sweat chloride and/or the genotype test are documented in the subject's medical record, and the historic genotype result is approved by the Vertex medical monitor, the tests do not need to be performed at screening. A sweat chloride test must be performed if the sweat chloride value is not available in the subject's medical records and the value is needed to establish eligibility.
3. An ivacaftor-responsive *CFTR* mutation on at least 1 allele. Subjects will be eligible in countries/regions where ivacaftor is approved for use in subjects 2 years of age and older.
  - If a genotype test has been performed previously and is documented in the subject's medical record, the subject's eligibility must be approved by the Vertex medical monitor. If a historic genotype result is not available at screening or if the historic genotype result is not approved by the Vertex medical monitor, the subject will undergo *CFTR* genotype screening and the results must be reviewed before the first dose of ivacaftor. Subjects who have been enrolled and whose screening genotype does not confirm study eligibility will not receive study drug.
4. Hematology, serum chemistry, and vital signs results have no clinically significant abnormalities that would confound the study assessments, as judged by the investigator.
5. Weight at screening must be within the weight limits as defined for the study drug dose levels (Section 9.2.2) or according to the dosing guidelines identified in the "Justification for Dose Selection" memorandum effective at the time a subject is screened.
6. For subjects <3 months of age only, gestational age  $\geq 38$  weeks.
7. As judged by the investigator, parent or legal guardian must be able to understand protocol requirements, restrictions, and instructions; and must sign the ICF.

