Measures of nutritional status: Poor somatic growth and poor nutritional status are common in patients with CF owing to a number of factors, including increased energy expenditures and appetite suppression due to lung disease as well as diabetes and pancreatic insufficiency-related fat malabsorption. Growth deficiencies in children as young as 2 years of age are associated with worsening lung function and are also independent predictors of mortality in children with CF. Furthermore, growth deficiencies at 4 months of age are most predictive of later growth deficiencies.

While it is unknown if poor weight gain predicts clinical lung disease or whether progressive lung disease leads to poor weight gain, change in weight is a clinically relevant endpoint. Given that ivacaftor is a systemic therapy, it has the potential to improve extrapulmonary manifestations of CF. Modulation of CFTR function in the pancreas and gastrointestinal tract may lead to improvements in digestion and, consequently, weight gain.

In Phase 3 Studies 102 and 103, the improvement in mean weight gain after 24 weeks of ivacaftor versus placebo treatment was substantial, clinically meaningful, and statistically significant in subjects  $\geq 12$  years of age (Study 102) and 6 to 11 years of age, inclusive (Study 103). In open-label Phase 3 Study 108, conducted in subjects 2 through 5 years of age, substantial improvements in nutritional status with ivacaftor treatment were observed for weight, weight-for-age z-scores, BMI, and BMI-for-age z-scores; these improvements continued to Week 24.

As children gain weight as part of normal growth, adjustment for age and sex is necessary to assess changes in nutritional status in a population of boys and girls in varying stages of growth. To evaluate the effect of ivacaftor on growth and nutrition adjusted for age and sex, weight-for-age, length-for-age, weight-for-length-for-age, and BMI-for-age z-scores will be determined.

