### **11.2 Subject and Disease Characteristics**

For subjects transitioning from Study 124 Part B, demographics, medical history, and historical data will be taken from Study 124. For all other subjects, demographics, medical history, length, weight, and the additional historical data described below will be collected before (e.g., at screening) or at Day 1.

The following historical data from birth to screening will also be collected:

- Maternal/pregnancy history: complications in pregnancy, gestational age at delivery, method of delivery
- Quarterly (approximately every 12 weeks) length and weight measurements
- The dates and reasons for all CF-related hospitalizations
- Any use (yes or no) of the following medications: inhaled tobramycin, inhaled aztreonam, inhaled colimycin, inhaled hypertonic saline, dornase alfa, ibuprofen, azithromycin, and pancreatic enzyme replacement therapy
- Historical pancreatic status measurements (prior fecal elastase-1 assessments)

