### 12.3.3.3 Analysis of Tertiary Variables

- Weight
- Length
- Weight-for-length
- Weight-for-age z-score
- Length-for-age z-score
- Weight-for-length-for-age z-score
- BMI
- BMI-for-age z-score

Data (including changes from baseline) will be summarized by either treatment duration or time on study and presented by treatment group (subjects from Study 124 Part B and subjects not from Study 124 Part B).

Weight, length, and weight-for-length, adjusted for sex and age, will be summarized as weight-for-age z-score, length-for-age z-score, and weight-for-length z-score, respectively. Z-scores will be calculated using the Nutrition Examination Survey (NCHS) Growth Chart Equations for children and adolescents 0 to 48 months of age.

- LCI (including changes from baseline) will be summarized by either treatment duration or time on study and presented by treatment for subjects who had their LCIs evaluated.
- Measure of pancreatic function (fecal elastase-1): This parameter will be summarized descriptively as a continuous parameter, and results (including changes from baseline) will be summarized by either treatment duration or time on study and presented by treatment.
- Markers of intestinal inflammation (e.g., fecal calprotectin): This parameter will be summarized descriptively as a continuous parameter, and results (including changes from baseline) will be summarized by either treatment duration or time on study and presented by treatment.
- Qualitative microbiology cultures: The presence of bacteria will be descriptively summarized by subject counts and percentages by visit and treatment. Shifts from baseline may be presented, as appropriate.
- Pulmonary exacerbations: Pulmonary exacerbations will be identified using the definitions provided in Section 11.5.3 and will be analyzed in 3 ways:
  - The number of pulmonary exacerbations will be normalized to an annual period to adjust for differences in time spent on study and summarized as a continuous variable using descriptive summary statistics and presented by treatment.

- The number of days with pulmonary exacerbations (cumulative duration) will be normalized to an annual period to adjust for differences in time spent on study and summarized as a continuous variable using descriptive summary statistics and presented by treatment.

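### Weight-for-age and length-for-age z-scores carry no gestational-age correction, so their change from baseline drifts upward in any child born preterm (minor)

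*SAP*

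**What the plan says.** **Derivation.** SAP 8.3.3.1 states that the weight-for-age, length-for-age, weight-for-length and BMI-for-age z-scores "will be derived from weight, length, and BMI values using the WHO Child Growth Standards". It does not say which age enters the calculation. Protocol 12.3.3.3 describes the measures as "Weight, length, and weight-for-length, adjusted for sex and age" and does not mention gestational age. Protocol 9.2.3 gives the reason for using z-scores: "adjustment for age and sex is necessary to assess changes in nutritional status".

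**Eligibility.** For subjects not from Study 124 Part B, Protocol 8.2.1 requires "Age <24 months at the Day 1 Visit". Criterion 6 begins "For subjects <3 months of age only, gestational age" and sets a minimum of 38 weeks. Section 8.2.2 has no exclusion for prematurity. For rollovers, the opening criterion of Protocol 8.1.1 is "Subjects transitioning from Study 124 Part B must have completed the last study visit of Study 124 Part B", and Section 8.1 has no gestational-age criterion.

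**Data held.** Protocol 11.2 collects "complications in pregnancy, gestational age at delivery, method of delivery". SAP 8.2.2 lists the same items as disease characteristics and makes no other use of them.

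**Analysis.** Change from baseline through Week 96 in these z-scores is a tertiary endpoint (SAP 5.1.3). It is summarized descriptively by visit for the ivacaftor arm overall (SAP 8.3 and 8.3.3.2). Rollovers are measured from their Study 124 baseline (SAP 8.1), so they were younger at that baseline than at Day 1 of this study.

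**The concern.** A child born several weeks early and scored at chronological age is compared with children who are that many weeks further from conception. In early infancy those weeks are a large part of growth, so the score is well below what the child's own curve warrants. By the third or fourth year of life the same weeks matter little. The score therefore climbs even if the child follows the reference curve for corrected age exactly.

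For weight-for-age and length-for-age the climb is always in the direction that looks like benefit. With no control arm, nothing in the planned summaries separates it from a drug effect. For these children the z-score then fails to do what Protocol 9.2.3 uses it for, which is to take normal growth out of the comparison.

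**Working it through.** The plan gives no figure to reproduce: the sample of about 75 has no effect size, SD or power behind it. The check therefore concerns the direction and rough size of the drift.

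**Inputs from the documents.** Week 96 is day 672, or 672 / 30.4375 = 22.08 months after Day 1. Entry age is under 24 months. About 75 subjects are planned.

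**Assumed inputs, not in the documents.** Approximate infant medians M and coefficients of variation CV; 2 to 8 weeks early; baseline at 3 to 23 months; 5% to 15% of the arm preterm.

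**Model.** A child lies exactly on the median for corrected age, with no treatment effect and no true catch-up. With g = weeks early × 7 / 30.4375 months, the score at chronological age t is

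z(t) = ln[M(t − g) / M(t)] / CV(t), and drift = z(b + 22.08) − z(b) for baseline age b.

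**Worked case: weight, 4 weeks early (g = 0.92), baseline 12 months.** The assumed medians are 8.9 kg at 9 months, 9.65 at 12, 13.3 at 30 and 14.3 at 36, interpolated linearly.

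- Baseline: ln(9.42 / 9.65) / 0.109 = −0.22.
- Week 96 (34.08 months): ln(13.83 / 13.98) / 0.120 = −0.09.
- Drift: −0.09 − (−0.22) = +0.13.

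**Drift to Week 96 per preterm child:**

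| Weeks early | Baseline (months) | Weight-for-age | Length-for-age | BMI-for-age |
|---|---|---|---|---|
| 4 | 3 | +0.94 | +1.17 | +0.41 |
| 4 | 6 | +0.34 | +0.54 | +0.02 |
| 4 | 12 | +0.13 | +0.31 | −0.07 |
| 4 | 18 | +0.08 | +0.22 | −0.07 |
| 4 | 23 | +0.06 | +0.15 | +0.01 |
| 6 | 3 | +1.63 | +1.90 | +0.85 |
| 6 | 12 | +0.20 | +0.46 | −0.10 |
| 8 | 3 | +2.45 | +2.68 | +1.34 |
| 8 | 18 | +0.15 | +0.45 | −0.14 |

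Over all 2-to-8-week scenarios the drift was positive throughout for weight-for-age (+0.03 to +2.45) and length-for-age (+0.08 to +2.68). BMI-for-age ran from −0.14 to +1.34. Weight-for-length does not use age, so its drift is 0. With corrected age at both visits, every drift in this model is 0.

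**Cross-check with a linear form.** Bias = −(velocity × weeks early / 4.345) / SD. Assume 0.70 kg/month and SD 0.75 kg at 4 months, and 0.19 kg/month and SD 1.4 kg at 28 months. Six weeks early gives −1.29 and −0.19, a gain of 1.10.

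**Arm mean.** Shift = preterm share × drift per child.

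- Low: 0.05 × 0.1 = 0.005.
- High: 0.15 × 1.10 = 0.165.
- All preterm baselines at 12 months, 4 to 6 weeks early: weight 0.05 × 0.13 = 0.0065 to 0.15 × 0.20 = 0.03; length 0.05 × 0.31 = 0.016 to 0.15 × 0.46 = 0.069.

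For scale, an assumed SD of 0.8 for the change gives a standard error of 0.8 / √75 = 0.09.

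**The case against.** **The plan does not state chronological age.** The SAP is silent on which age is used, and SAP 8.1 refers to an internal document of programming rules that is not available here. A correction might sit there. This stands as a limit on the claim, but chronological age is the natural reading of a plan that mentions only age and sex. A rule that changes an endpoint belongs in the SAP.

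**Not all growth z-scores are affected.** A reader might infer that every growth z-score drifts upward. That does not follow: weight-for-length z is free of the artefact and is already a planned endpoint, and BMI-for-age changes sign with baseline age.

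**Few children may be involved.** Preterm eligibility is shown only for subjects not from Study 124 Part B; the entry rules of Study 124 are not in these documents. Exclusion criterion 1 in Protocol 8.2.2 also lets the investigator keep out a child whose condition might confound the results. Study 124 opens with ages 12 to under 24 months (Protocol 9.1), where the drift is modest. A reader might infer that the reported growth gain will be materially inflated. The documents do not support that, since they give neither the number of preterm children nor their baseline ages.

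**The figures are external.** The growth medians, the preterm share and the SD are all assumed. This stands for the size. The direction for weight and length rests on growth slowing with age and not on the exact values.

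**Readers can see who was preterm.** Gestational age is summarized and individual data are listed. That shows that preterm children are present but does not correct the mean.

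**Conclusion.** The point holds for weight-for-age and length-for-age. Under the natural reading of SAP 8.3.3.1, any child born preterm contributes an upward change by Week 96 that is unrelated to treatment. The change is largest for early baselines, and the single-arm design cannot remove it. The effect on the arm mean is roughly 0.005 to 0.165 z if 5% to 15% are preterm and each drifts by 0.1 to 1.1 z.

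This range is illustrative and not a bound. Its upper end needs 15% preterm, all about 6 weeks early with a baseline near 4 months. Still younger or more preterm children would exceed it, and late baselines would fall below it. With 12-month baselines the weight-for-age shift is at most about 0.03 z in the cases worked, well under the assumed standard error of 0.09.

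Severity is minor. The endpoints are tertiary and descriptive, no inference is planned, and the primary safety objective is untouched.

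**What to change.** In SAP 8.3.3.1:

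- State the age used for the age-based z-scores.
- For children born before 37 weeks, derive these scores at age corrected for gestational age, on the same basis at baseline and at every visit through Week 96.
- Report the number born preterm.
- Give two sensitivity summaries: the result at chronological age, and the result without preterm children.

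The correction should not stop at 24 months. A preterm child who enters under Protocol 8.2.1 is at least 3 months old, so is at least 3 + 22.08 = 25.08 months old at Week 96. Baseline would then be corrected and Week 96 not, which builds in a spurious fall. In the model with a 3-month baseline, 4 to 6 weeks early, that fall is −0.13 to −0.19 z for weight and −0.21 to −0.33 z for length.

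The cost is a short addition to the SAP, one derived age variable and two extra summaries. Gestational age is already collected, so no new data are needed. If few children are preterm, the sensitivity summaries will show that the issue is negligible.

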8.3.3.2 Tertiary Analysis

- The following growth parameters will be summarized descriptively as continuous variables by visit (including change from baseline).
 - Weight
 - Length
 - Weight-for-length (expressed as a percentile)
 - BMI
 - Weight-for-age z-score
 - Length-for-age z-score
 - Weight-for-length z-score
 - BMI-for-age z-score

Summary statistics for weight-for-age, length-for-age, and BMI-for-age percentiles may also be provided to aid interpretation of z-scores.

- LCI_{2.5} will be analyzed as a continuous variable using descriptive summary statistics and results (including changes from baseline) presented by visit. In the event that fewer than 3 subjects have these optional assessments available, listings of results may be provided instead of summary statistics.
- Markers of pancreatic inflammation (fecal elastase-1): These parameters will be summarized descriptively as a continuous parameter and results (including changes from baseline) presented by visit. Shifts from baseline will be summarized by visit.
- Marker of intestinal inflammation (fecal calprotectin). This parameter will be summarized descriptively as a continuous parameter and results (including changes from baseline) presented by visit.
- Qualitative microbiology cultures: the presence of bacteria will be descriptively summarized by subject counts and percentages by visit. Shifts from baseline may be presented, as appropriate.
- Pulmonary exacerbations: Pulmonary exacerbations (PE_x) will be identified using the definitions provided in Section 11.5.3 of the protocol, and will be analyzed in 3 ways, as follows:
 - The number of pulmonary exacerbations will be normalized to an annual period to adjust for differences in time spent on study and summarized as a continuous variable using descriptive summary statistics.
 - The number of days with pulmonary exacerbations (cumulative duration) will be normalized to an annual period to adjust for differences in time spent on study and summarized as a continuous variable using descriptive summary statistics.

- The time-to-first pulmonary exacerbation in 96 weeks, total treatment duration will be analyzed using the Kaplan-Meier method (provided the number of subjects with events observed is adequate) and the event-free rate.
- Rate of CF-related hospitalizations will be analyzed in 3 ways, as follows:
 - The number of CF-related hospitalizations will be normalized to an annual period to adjust for differences in time spent on study and analyzed as a continuous variable using descriptive summary statistics.
 - The number of days hospitalized (cumulative duration) will be normalized to an annual period to adjust for differences in time spent on study and summarized as a continuous variable using descriptive summary statistics.
 - The time-to-first CF-related hospitalization in 96 weeks, total treatment duration will be analyzed using the Kaplan-Meier method (provided the number of subjects with events observed is adequate) and the event-free rate.

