subsequent growth delay, poorer cognitive development, and other clinical comorbidities such as decreased lung function and survival. Studies of subjects 1 month through 6 years of age also show the presence of lung disease and liver disease. High-resolution computed tomography studies including infants with CF that were diagnosed by newborn screening, but were considered clinically healthy, indicate that structural lung damage is common even very early in disease progression. In a cohort of 81 well-treated CF patients in Australia, by 3 years, 10% had *Pseudomonas aeruginosa* infection and 84% had evidence of bronchiectasis. This is consistent with the results of inflammatory marker studies that have found that airway inflammation begins in infancy. The presence of airway inflammation in infancy signals the beginning of the destructive cycles of chronic inflammation, infection, and irreversible lung damage that are characteristic of CF lung disease. A study of the longitudinal development of *P. aeruginosa* infection in children with CF found that 29% of the infants followed developed nonmucoid infection in the first 6 months of life; overall, the median age for nonmucoid *P. aeruginosa* infection was 1.0 years and for the transition from nonmucoid to mucoid *P. aeruginosa* infection was 13.0 years. Mucoid *P. aeruginosa* infection is considered the major limiting factor in survival for patients with CF.

Poor somatic growth and poor nutritional status are common in patients with CF owing to a number of factors, including exocrine pancreatic insufficiency, increased energy expenditure and appetite suppression due to lung disease, as well as diabetes. Notably, 18% of children with CF fall below the US Centers for Disease Control and Prevention's (CDC) fifth percentile for weight, and 16% of children fall below the CDC fifth percentile for height. Malnourishment is associated with worsening lung function in children with CF and is also an independent predictor of mortality in this population.

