#### **7.1.3 Tertiary Endpoints**

- Absolute change from baseline through Week 96 for the following endpoints:
  - Weight
  - Length (assessed as height, as age appropriate)
  - Weight-for-length
  - Weight-for-age z-score
  - Length-for-age z-score
  - Weight-for-length-for-age z-score
  - BMI
  - BMI-for-age z-score
  - Lung clearance index (LCI) at qualified study sites
  - Fecal elastase-1
  - Markers of intestinal inflammation
  - Qualitative microbiology cultures
- Annualized rate of pulmonary exacerbations
- Rate of CF-related hospitalizations

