Qualitative microbiology cultures: Microbiological endpoints, such as bacterial colony counts and selection of resistant bacterial strains, are well-established endpoints used to evaluate antimicrobial therapies in CF. Because compounds such as ivacaftor that restore CFTR function may increase hydration of airway secretions and lead to a decrease in acquisition of bacteria in the CF airway, acquisition of bacteria is included as a tertiary endpoint in this study. Because the majority of subjects  $< 24$  months of age do not expectorate spontaneously, oropharyngeal swabs will be used to obtain airway cultures in this study.

Pulmonary exacerbations and CF-related hospitalizations: Pulmonary exacerbations are used to assess efficacy in therapies targeting improvement in CF disease. These events have been associated with the severity and rate of progression of lung disease in patients with CF. To date, however, there is no generally accepted objective definition of an exacerbation, and large multicenter CF clinical studies have used many variations of physician-derived definitions in patients 6 years of age and older. Despite the lack of a standard definition, reduction in exacerbation rate has served as a key clinical efficacy measure in definitive CF clinical studies, supporting the registration of 2 chronic CF pulmonary therapies. Definitions for pulmonary exacerbation in subjects  $< 24$  months of age are being evaluated in ongoing studies of CF therapies, but they have not yet been validated for use in clinical studies involving subjects of

this age. In this study, pulmonary exacerbation has been defined based on modification of criteria used in previous and ongoing trials in young children with CF, and occurrence will be derived based on both primary and alternative definitions. In addition, data on CF-related hospital admissions will be collected to assess the rate of these clinically significant events.

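### The protocol rationale makes acquisition of airway bacteria a tertiary endpoint, but the committed analysis is prevalence by visit, which does not identify acquisition

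*SAP*

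**What the plan says.** Protocol 9.2.3 explains why oropharyngeal cultures are taken: restoring CFTR function may reduce the acquisition of bacteria in the airway, and "acquisition of bacteria is included as a tertiary endpoint in this study".

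The formal lists do not use that word. Protocol 7.1.3 and SAP 5.1.3 put qualitative microbiology cultures under "Absolute change from baseline through Week 96 for the following endpoints".

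The analysis sections commit to something else again. Protocol 12.3.3.3: "The presence of bacteria will be descriptively summarized by subject counts and percentages by visit and treatment". SAP 8.3.3.2 repeats this for the pooled ivacaftor arm: "the presence of bacteria will be descriptively summarized by subject counts and percentages by visit. Shifts from baseline may be presented, as appropriate". Within-child change is thus optional in the SAP, and the protocol also leaves shifts optional.

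Other endpoints in SAP 8.3.3.2 get firmer commitments. For fecal elastase-1, "Shifts from baseline will be summarized by visit". Pulmonary exacerbations and CF-related hospitalizations get Kaplan-Meier time-to-first analyses, provided there are enough events.

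Neither document defines acquisition, an at-risk group negative at baseline, the organisms to be reported, or a summary of first positive cultures.

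**The concern.** Acquisition is a within-child event: a positive culture for an organism in a child who did not have it before. A by-visit percentage is a cross-section of all children cultured at that visit, including those already positive at baseline. A flat series of percentages could come from a few persistently colonized children or from many children turning positive and clearing. The two patterns mean different things for the question in Section 9.2.3, and the committed table cannot tell them apart.

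The same table also falls short of the listed endpoint. Comparing a visit with baseline gives at most a net change in the group percentage, in which gains and losses cancel. Only the optional shifts would show change within children.

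**Working it through.** **Nothing to reproduce.** The plan gives no culture rate, no target and no calculation for this endpoint.

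**Inputs from the documents**
- n = about 75 (Protocol 12.1, SAP 6.2).
- Scheduled post-baseline cultures: k = 4 for rollover subjects (Weeks 24, 48, 72, 96; Protocol Tables 3-1 and 3-2) and k = 5 for subjects not from Study 124 Part B (Weeks 12, 24, 48, 72, 96; Table 3-3).

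**Assumptions.** Complete cultures; x children positive at every post-baseline visit. The values of x are illustrative, because the documents give no prevalence.

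**Bounds on the number ever positive after baseline**
- Minimum (same children each time): x.
- Maximum (different children each time): min(n, k·x).

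| x/75 at every visit | 4 visits | 5 visits |
|---|---|---|
| 4 (5.3%) | 4 to 16 (5.3% to 21.3%) | 4 to 20 (5.3% to 26.7%) |
| 8 (10.7%) | 8 to 32 (10.7% to 42.7%) | 8 to 40 (10.7% to 53.3%) |
| 11 (14.7%) | 11 to 44 (14.7% to 58.7%) | 11 to 55 (14.7% to 73.3%) |
| 15 (20.0%) | 15 to 60 (20.0% to 80.0%) | 15 to 75 (20.0% to 100%) |

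In each cell, every value in the range gives the same post-baseline by-visit table.

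**From ever positive to acquisition.** The table bounds acquisition only if every child is negative at baseline. Suppose instead that 15 of 75 are positive at baseline and at each of four visits, so that 75 − 15 = 60 are at risk. If the same 15 are positive throughout, acquisition is 0/60. If each visit brings 15 new children from the 60, it is 4 × 15 = 60, or 60/60. Showing the baseline percentage therefore does not settle the matter.

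**What the windowing rules add**
- Microbiology is classed as an efficacy assessment in SAP Appendix B. When a window holds several records, the scheduled-visit record is used (SAP 8.1). A positive unscheduled culture then drops out of the table if the scheduled culture in that window is negative.
- The windows are long: for rollover subjects, Week 24 covers days 2 to 252 (252 − 2 + 1 = 251 days) and Week 48 covers days 253 to 420 (168 days).
- For rollover subjects, baseline is the parent-study baseline and the first window starts on day 2 (SAP Table 11-4). The Study 126 Day 1 culture falls in no analysis window. A child who turned positive during Study 124 would first show as positive in the Week 24 window.

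**The case against.** The strongest reply is that acquisition as an endpoint rests on one sentence of the rationale. The operative sections, Protocol 12.3.3.3 and SAP 8.3.3.2, agree with each other, so the SAP has not departed from the protocol's analysis. All individual data will be listed (SAP 7.1.1 and 8.1), so first positives could be worked out by hand for about 75 children. The endpoint is tertiary in an uncontrolled study with no power claim. All of this stands and keeps the priority low. It does not close the gap: a listing is not a planned summary, and the committed table matches neither the rationale nor the listed change from baseline.

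A reader might infer four stronger things that the documents do not support.
- **That the plan fails a comparison with natural history.** Protocol 5.2 reports that "29% of the infants followed developed nonmucoid infection in the first 6 months of life". That is disease background, tied to age, and nowhere named as a comparator. Children here may enter at any age under 24 months, so first positivity by study visit would not line up with it.
- **That shift tables would hide a positive culture that clears.** A child positive at Week 24 and negative at Week 96 would appear in a Week 24 shift. The weakness of the shifts is that they are optional and not cumulative.
- **That 15 to 60 is a range for acquisition.** It is a range for ever positive; acquisition could be 0.
- **That a better table would show reduced acquisition.** Without a control group it can describe acquisition but not a decrease.

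**Conclusion.** The point holds in limited form. Followed as written, the plan yields point prevalence, which identifies neither the acquisition named in Protocol 9.2.3 nor the within-child change implied by Protocol 7.1.3 and SAP 5.1.3. The inconsistency begins in the protocol and is carried into the SAP.

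How much is lost depends on culture rates the documents do not give. At an assumed 15/75 per visit over four visits with complete cultures, one table fits 15 to 60 children ever positive; at 8/75 it fits 8 to 32. In either case acquisition could be nil if the positives were already there at baseline.

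Severity is low. The effect is on what a tertiary, descriptive result can be taken to mean; no primary or secondary conclusion, error rate or sample size changes. The change is worth making because it is cheap.

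**What to change.** In SAP 8.3.3.2:
1. Keep the by-visit table and make the shift table a commitment.
2. Name the pathogens to be reported, *P. aeruginosa* at least. For each, add one table: among children culture-negative for it at baseline, the number and percentage with a first positive culture at any post-baseline visit through Week 96, and the visit of first positivity. Use all cultures, including unscheduled ones, instead of one record per window.
3. Present it separately for rollover and ivacaftor-naive subjects, because they have four and five scheduled post-baseline cultures and a pooled figure would mix the two.
4. For rollover subjects, choose one rule and state it. Either require negative cultures at both the Study 124 baseline and Study 126 Day 1, or count from the Study 124 baseline and include Study 124 on-treatment cultures. The second option depends on Study 124's culture schedule, which these documents do not give.
5. Report the number of cultures contributing, since missing ones are not imputed (SAP 8.1).
6. Label the result as first positive since baseline. Earlier cultures are not among the historical data collected (Protocol 11.2), so it cannot be called first ever.

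The cost is SAP wording, the rollover decision and one table per pathogen, with no new samples or visits. Separate presentation departs from the SAP's pooled reporting, for this table only. Two limits remain: first positivity is known only to within the 12- to 24-week interval between scheduled cultures, and the summary stays uncontrolled.
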